8.3.3 CLASSIFICATION OF AN ADVERSE EVENT

8.3.3.1 SEVERITY OF EVENT

For adverse events (AEs) not included in the protocol defined grading system, the following guidelines will be used to describe severity.

Mild – Events require minimal or no treatment and do not interfere with the participant’s daily activities.

Moderate – Events result in a low level of inconvenience or concern with the therapeutic measures. Moderate events may cause some interference with functioning.

Severe – Events interrupt a participant’s usual daily activity and may require systemic drug therapy or other treatment. Severe events are usually potentially life-threatening or incapacitating. Of note, the term “severe” does not necessarily equate to “serious”.

8.3.3.2 RELATIONSHIP TO STUDY INTERVENTION/EXPERIMENTAL MANIPULATION

All adverse events (AEs) will have their relationship to study procedures, including the intervention, assessed by an appropriately trained clinician based on temporal relationship and his/her clinical judgment. The degree of certainty about causality will be graded using the categories below.

Related – The AE is known to occur with the study procedures, there is a reasonable possibility that the study procedures caused the AE, or there is a temporal relationship between the study procedures and the event. Reasonable possibility means that there is evidence to suggest a causal relationship between the study procedures and the AE.

Not Related – There is not a reasonable possibility that the study procedures caused the event, there is no temporal relationship between the study procedures and event onset, or an alternate etiology has been established.

8.3.3.3 EXPECTEDNESS

Given the sensitivity of the questions being asked regarding violence perpetration, we are taking extra precautionary measures with an internal data safety and monitoring plan in place, described above. All research personnel are trained on the emotional distress protocol and complete training on child abuse reporting requirements. Each neighborhood/site has a designated point RA, who along with the research coordinator, is connected to the community site leads and can identify concerns about data collection or participant safety.

A Summary Report of the Data and Safety Monitoring Plan will be submitted with the annual IRB renewal.

8.3.4 TIME PERIOD AND FREQUENCY FOR EVENT ASSESSMENT AND FOLLOW-UP

The occurrence of an adverse event (AE) or serious adverse event (SAE) may come to the attention of study personnel during study visits and interviews of a study participant.

Should a participant disclose safety concerns during the course of programming or study procedures, the site RA follows the emotional distress protocol and immediately notifies [name] (PI), a plan for safety and any reporting requirements are addressed, and the RA completes a report. Such events are reported to the IRB.

All AEs occurring while on study will be documented appropriately regardless of relationship. All AEs will be followed to adequate resolution.

8.3.5 ADVERSE EVENT REPORTING

Review and report any adverse events associated with the study to the IRB.

8.3.6 SERIOUS ADVERSE EVENT REPORTING

In consultation with the PI, a trained member of the study team will be responsible for conducting an evaluation of a serious adverse event and shall report the results of such evaluation to the NIH and the reviewing Institutional Review Board (IRB) as soon as possible, but in no event later than 10 working days after the investigator first learns of the event.

8.3.7 REPORTING EVENTS TO PARTICIPANTS

N/A

8.3.8 EVENTS OF SPECIAL INTEREST

N/A

8.3.9 REPORTING OF PREGNANCY

N/A

8.4 UNANTICIPATED PROBLEMS

8.4.1 DEFINITION OF UNANTICIPATED PROBLEMS

This protocol uses the definition of Unanticipated Problems as defined by the Office for Human Research Protections (OHRP). OHRP considers unanticipated problems involving risks to participants or others to include, in general, any incident, experience, or outcome that meets all of the following criteria:

- Unexpected in terms of nature, severity, or frequency given (a) the research procedures that are described in the protocol-related documents, such as the Institutional Review Board (IRB)-approved research protocol and informed consent document; and (b) the characteristics of the participant population being studied;
- Related or possibly related to participation in the research (“possibly related” means there is a reasonable possibility that the incident, experience, or outcome may have been caused by the procedures involved in the research); and
- Suggests that the research places participants or others at a greater risk of harm (including physical, psychological, economic, or social harm) than was previously known or recognized.

8.4.2 UNANTICIPATED PROBLEMS REPORTING

The investigator will report unanticipated problems (UPs) to the reviewing Institutional Review Board (IRB) and to the Data Coordinating Center (DCC)/lead principal investigator (PI). The UP report will include the following information:

- Protocol identifying information: protocol title and number, PI’s name, and the IRB project number
- A detailed description of the event, incident, experience, or outcome
- An explanation of the basis for determining that the event, incident, experience, or outcome represents an UP
- A description of any changes to the protocol or other corrective actions that have been taken or are proposed in response to the UP

To satisfy the requirement for prompt reporting, UPs will be reported using the following timeline:

- UPs that are serious adverse events (SAEs) will be reported to the IRB and to the DCC/study sponsor/funding agency within 2 days of the investigator becoming aware of the event
- Any other UP will be reported to the IRB and to the DCC/study sponsor/funding agency within 10 days of the investigator becoming aware of the problem
- All UPs should be reported to appropriate institutional officials (as required by an institution’s written reporting procedures), the supporting agency head (or designee), and the Office for Human Research Protections (OHRP) within 10 days of the IRB’s receipt of the report of the problem from the investigator

8.4.3 REPORTING UNANTICIPATED PROBLEMS TO PARTICIPANTS

N/A

9 STATISTICAL CONSIDERATIONS

9.1 STATISTICAL HYPOTHESES

Aim 3: To pilot test the feasibility and acceptability of the adapted YES intervention compared to a control intervention (Job Skills) among adolescents and their key adult supports at four community-based sites.

Approach: Participant tracking and post-intervention surveys will assess feasibility and acceptability.. Exploratory outcomes will include changes between pre-and post-intervention assessments of social network structure, relationship quality, social support (emotional and instrumental), attitudes towards violence, and violence involvement.

Primary Outcome Measure:

1. Participant Attendance: Attendance is recorded at the beginning and end of each session. Calculated as a proportion of total number of sessions attended (possible session attended #: 0-12 for youth participants and 0-10 for adult participants; possible proportion attended range: 0-1). [Time Frame: through intervention completion, 12 weeks]

2. Participant Satisfaction: At the end of the program, participants will be asked about how satisfied they were overall with the topics discussed and format of the program using 5-point Likert scale items. Means score will be calculated across the items (possible range: 1-5; higher score means higher satisfaction). [Time Frame: end of program (12 weeks)]

Secondary Outcome Measure:

3. Participant Satisfaction: At the end of each weekly session, participants will be asked about how satisfied they were with the topics discussed for that session using 5-point Likert scale items. Means score will be calculated (possible range: 1-5; higher score means higher satisfaction). [Time Frame: weekly for 12 weeks]

Other Pre-specified Outcome Measures:

4. Change in social network composition: Participants will complete an abbreviated social network survey that asks them to identify key sources of emotional and instrumental support, and to characterize the nature of these relationships (network size, network density, mean link strength). [Time Frame: Baseline, end of program (12 weeks)]

5. Change in violence perpetration: Summary score of past 30-day youth violence perpetration adapted from the Aggressive Behavior-SAGE Baseline survey (9 items, each measured on a 5-point frequency scale from 0 times to 7 or more times). Violence perpetration items will be added to create a summary violence perpetration score with 1 point for each response of at least 1 time (possible range: 0-9; lower score indicates better outcome). [Time Frame: Baseline, end of program (12 weeks)]

6. Change in violence victimization: Summary score of past 30-day youth violence victimization adapted from the Victimization-Problem Behavior Frequency Scale (9 items, each measured on a 5-point frequency scale from 0 times to 7 or more times). Violence victimization items will be added to create a summary violence victimization score with 1 point for each response of at least 1 time (possible range: 0-9; lower score indicates better outcome). [Time Frame: Baseline, end of program (12 weeks)]

7. Change in attitudes towards violence: Modified from the Children's Perception of Environmental Violence Scale, 6 items assessed on 5-point Likert scale, calculated as a mean score (possible range 1-5; lower score indicates better outcome). [Time Frame: Baseline, end of program (12 weeks)]

8. Change in coping: Modified from the Healthy Pathways Child-Report Scales: Active Coping Scale, 7 items assessed on 5-point Likert scale, calculated as a mean score (possible range 1-5; higher score indicates better outcome). [Time Frame: Baseline, end of program (12 weeks)]

9. Change in future orientation: Modified from the California Healthy Kids Survey, 7 items assessed on 5-point Likert scale, calculated as a mean score (possible range 1-5; higher score indicates better outcome). [Time Frame: Baseline, end of program (12 weeks)]

9.2 SAMPLE SIZE DETERMINATION

As previously described, the primary endpoints for this cluster-randomized feasibility trial are feasibility and acceptability among a sample of 50 adolescents and 25 adult participants. As such, point and interval estimation will be utilized for parameter estimation. Assuming 25 adolescents with complete data in each arm and a 5% type I error rate, we will have the ability to estimate within-arm 95% confidence interval margin-of-errors of no more than 0.20 for the proportion of participants achieving these feasibility and acceptability outcomes. We will additionally examine intraclass correlation coefficients (ICC) for all youth across 4 sites and for all adults at 2 sites; these ICCs will inform power and sample size calculations for a future R01 cluster-randomized intervention trial.

9.3 POPULATIONS FOR ANALYSES

All analyses will use an intention to treat approach and include all participants with available data. Primary outcomes will be estimated within each study arm using point estimates and 95% confidence intervals.

9.4 STATISTICAL ANALYSES

9.4.1 GENERAL APPROACH

Descriptive statistics will characterize participants' demographics and baseline survey responses. T tests, Wilcoxon rank sum tests, and chi square tests will assess for differences in baseline characteristics and baseline survey responses among intervention versus control participants, after accounting for clustering. Feasibility and acceptability will be the primary outcomes of the pilot trial. Both feasibility/acceptability

and exploratory outcomes will be estimated within each study arm using point estimates and 95% confidence intervals. We will examine these endpoints separately for youth and adults. As an exploratory measure, we will assess outcomes on the difference between pre- and post-intervention measures of social network metrics, relationship quality and communication, attitudes towards violence, conflict resolution and coping, and future orientation between intervention and control participants. We will utilize generalized linear mixed models to account for site-level clustering. Missing data will be managed with multiple imputation if the mechanism of missingness is ignorable. Interview transcripts will be coded and analyzed by two independent reviewers through content analysis to identify themes related to intervention acceptability and satisfaction.

9.4.2 ANALYSIS OF THE PRIMARY ENDPOINT(S)

The primary outcome measures for this study are participant attendance (feasibility) and participant satisfaction (acceptability). Both feasibility and acceptability and exploratory outcomes will be estimated within each study arm using point estimates and 95% confidence intervals. We will examine these endpoints separately for youth and adults.

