1 PROTOCOL SUMMARY

1.1 SYNOPSIS

Title:	Strengthening Adolescent-Adult Networks to Reduce Youth Violence
Grant Number:	1K23HD098277-01
Study Description:	This community-partnered cluster-randomized trial will examine the feasibility and acceptability of a social network-based youth violence prevention program called Strengthening Connections for Change for youth ages 13-17 and their key adult supports. Set in four lower resource Pittsburgh, Pennsylvania neighborhoods, this study brings together youth ages 13-17 and their self-identified key adult supports to focus on leadership, strengthening intergenerational networks, community engagement, and violence prevention.
Objectives[*]:	The primary goal is to test the feasibility and acceptability of the adapted Youth Empowerment Solutions intervention (Strengthening Connections for Change, SCC) compared to a control intervention (Job Skills) delivered over 12 weekly sessions through a cluster-randomized community-based trial among adolescents, ages 13- 17 (n=50 youth, 25 in intervention group and 25 in control group) and their key adult supports (n=25 in intervention group) at four community-based sites (2 intervention and 2 control sites) in Pittsburgh, PA. As this is a feasibility trial, the primary end points are feasibility and acceptability.
Endpoints[*]:	Primary outcomes will include feasibility and acceptability. Feasibility is defined by participant attendance calculated as a proportion of total number of sessions attended (possible session attended #: 0-12 for youth participants and 0-9 for adult participants; possible proportion attended range: 0-1). Acceptability is defined as overall satisfaction with curriculum content and format among youth (intervention and control) and among adults (intervention) measured at the end of programming. Secondary outcome measures include assessment of participant satisfaction on weekly session feedback forms. Exploratory outcomes include changes between pre-and post-intervention assessments of social network-level measures (e.g., network size, network density, mean link strength), attitudes towards violence, conflict resolution and coping, future orientation, and violence experiences.
Study Population:	Youth between the ages of 13 and 17 who live or attend programming within randomized neighborhood boundaries and their self-identified key adult supports.
Phase[*] or Stage:	N/A

**Description of
Sites/Facilities Enrolling
Participants:**

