6 STUDY INTERVENTION(S) OR EXPERIMENTAL MANIPULATION(S)

6.1 STUDY INTERVENTION(S) OR EXPERIMENTAL MANIPULATION(S) ADMINISTRATION

6.1.1 STUDY INTERVENTION OR EXPERIMENTAL MANIPULATION DESCRIPTION.

This pilot community-partnered cluster-randomized trial will examine the feasibility and acceptability of a social network-based youth violence prevention program called Strengthening Connections for Change for youth ages 13-17 and their self-identified key adult supports to focus on leadership, strengthening intergenerational networks, community engagement, and violence prevention. The study will be located in four lower resource Pittsburgh, Pennsylvania neighborhoods ('clusters') randomized to receive either the Strengthening Connections for Change program (i.e. intervention neighborhoods) or to a job skills training program (i.e. control neighborhoods). Randomization will occur 1:1 at the site level (2 intervention and 2 control sites). The study team will then work with each community-based site to recruit youth already engaged with the respective community site into the program to which each site has been randomized. The Strengthening Connections for Change intervention will be delivered weekly by research staff in twelve 2-hour sessions at community sites. The first 2 sessions will include youth-specific programming. For session 3-12, youth and adults will participate in separate programming for the first hour, then participate in a joint session.

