9.4.9 EXPLORATORY ANALYSES

As an exploratory measure, we will assess outcomes on the difference between pre- and post-intervention measures of social network metrics, including network size, density, and mean link strength, as well as violence perpetration, violence victimization, attitudes towards violence/retaliation, coping, and future orientation. We will utilize generalized linear mixed models to account for site-level clustering and include selected covariates. Missing data will be managed with multiple imputation if the mechanism of missingness is ignorable. Given the small sample and exploratory nature of the additional analyses, each exploratory test will utilize $\alpha=0.1$ for the threshold of significance, and no corrections will be made for multiple tests.

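### No allowance for site is stated for the primary within-arm 95% intervals although each arm is only two sites, so they will overstate precision beyond those sites if youth are treated as independent and the intraclass correlation is above zero.

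*Combined protocol and SAP*

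**What the plan says.** The primary analysis is estimation within arm. Section 9.4.2 says that the feasibility, acceptability and exploratory outcomes "will be estimated within each study arm using point estimates and 95% confidence intervals". Section 9.3 repeats it: "Primary outcomes will be estimated within each study arm using point estimates and 95% confidence intervals". Neither section mentions site.

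Allocation is by cluster. Section 6.1.1: "Randomization will occur 1:1 at the site level (2 intervention and 2 control sites"). The synopsis gives "n=50 youth, 25 in intervention group and 25 in control group", and 25 adults, all in the intervention arm and so at two sites.

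Clustering appears in four other places:

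- Sections 9.4.1 and 9.4.5 account for it when baseline characteristics are compared between arms.
- Section 9.4.9 attaches it to the exploratory outcomes: "We will utilize generalized linear mixed models to account for site-level clustering and include selected covariates".
- Section 9.4.1 also has a sentence on mixed models for site that names no outcome. It comes directly after the sentence on exploratory pre-post differences.
- Section 9.2 plans to examine ICCs for youth at four sites and adults at two, to inform a future trial.

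Section 9.2 also states the planned precision: "Assuming 25 adolescents with complete data in each arm and a 5% type I error rate", the plan expects "within-arm 95% confidence interval margin-of-errors of no more than 0.20" "for the proportion of participants achieving these feasibility and acceptability outcomes".

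**The concern.** Both programs are run as group discussions at community sites. Youth are recruited from those already engaged with a site, and peers invite peers (Sections 5.5 and 6.1.1). Attendance and satisfaction are therefore plausibly correlated within site. An interval that treats about 25 youth in two groups as 25 independent observations omits the between-site part of the variance.

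The point estimate and interval in each arm are the whole primary result, and they are meant to guide a larger trial. If the interval is too narrow, feasibility and acceptability look better established than they are. With two sites, one strong or weak site can also drive the arm figure, and Section 9.4.2 plans no site-level results that would show which one.

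**Working it through.** **Inputs.** 25 youth per arm and 95% confidence (Section 9.2). Two sites per arm (Section 6.1.1). Average site size m = 50/4 = 12.5, assuming equal sites; 25 adults at two sites also give 12.5. No ICC and no standard deviations are given. The ICC values 0 to 0.20 below are my assumption.

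**The plan's own figure.** Section 9.2 gives no expected proportion, so I take the worst case, p = 0.5:

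1.96 × √(0.5 × 0.5 / 25) = 1.96 × 0.10 = 0.196.

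This agrees with the stated limit of 0.20, but only as 25 independent youth (design effect 1). The planned precision therefore contains no allowance for site.

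**With clustering.** Design effect DE = 1 + (m − 1) × ICC = 1 + 11.5 × ICC. Effective sample size = 25/DE. Half-width = 0.196 × √DE. Coverage of the unadjusted interval ≈ 2Φ(1.96/√DE) − 1. The last column is a simulation of a normal outcome in one arm with sites of 13 and 12 and an unadjusted t interval on 24 df (200,000 runs per ICC).

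| ICC (assumed) | DE | Effective n | √DE | Half-width, p = 0.5 | Coverage, formula | Coverage, simulated |
|---|---|---|---|---|---|---|
| 0 | 1.000 | 25.0 | 1.00 | 0.196 | 95.0% | 95.0% |
| 0.01 | 1.115 | 22.4 | 1.06 | 0.207 | 93.7% | 93.7% |
| 0.05 | 1.575 | 15.9 | 1.25 | 0.246 | 88.2% | 88.3% |
| 0.10 | 2.150 | 11.6 | 1.47 | 0.287 | 81.9% | 81.8% |
| 0.20 | 3.300 | 7.6 | 1.82 | 0.356 | 71.9% | 70.6% |

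The half-widths are for a proportion. Attendance and mean satisfaction have no stated standard deviation, so the loss cannot be put in their units, but the factor √DE applies to them too. It slightly understates the shortfall, because the standard deviation computed from two sites also shrinks: at ICC 0.20 the ratio is about 1.82/√((25 − 3.30)/24) = 1.91.

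**Does a mixed model repair it?** Simulations with a normal outcome, sites of 12 and 13 in each arm, a random site effect, Wald limits and 40,000 runs per ICC:

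| ICC (assumed) | One-arm model: coverage | Site variance set to zero | Four-site model: coverage | Site variance set to zero |
|---|---|---|---|---|
| 0.01 | 94.3% | 65% | 94.9% | 58% |
| 0.05 | 90.4% | 55% | 92.0% | 45% |
| 0.10 | 86.5% | 48% | 88.8% | 34% |
| 0.20 | 81.2% | 37% | 85.4% | 22% |

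When the site variance is estimated as zero, the model returns essentially the unadjusted interval. A t quantile on 2 df in the four-site model goes the other way, with coverage of about 99% or more. A site-level interval within one arm has 1 df (t = 12.71), which gives a half-width of 12.71 × 0.10 = 1.27 for a proportion even at ICC 0, so it is uninformative.

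**Does widening by √DE repair it?** With the true ICC inserted, coverage is 94.9%, 94.6%, 94.4% and 93.7% at ICC 0.01, 0.05, 0.10 and 0.20.

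**The case against.** The strongest reply is that silence in Sections 9.3 and 9.4.2 is not a decision to ignore site. The mixed-model sentence in Section 9.4.1 stands under the general approach, in the same paragraph as the primary estimation, and names no outcome. Section 9.4.5 allows covariates in the primary analyses, which suggests some model. A reader might infer that the plan rules out any site adjustment; the documents do not support that. What they support is that none is stated for these intervals and that the scope of the 9.4.1 sentence is open. Its position after the exploratory sentence, and its repetition in Section 9.4.9 for the exploratory outcomes, make exploratory-only the more natural reading.

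A reader might also infer that a mixed model would be useless here. That goes too far: a model over all four youth sites covers clearly better than the unadjusted interval. It still falls short with Wald limits, and it is not available for adults, who are at two sites in all.

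The ICCs promised in Section 9.2 will give some view of between-site variation. They do not show which site drives an arm, and nothing says they will widen the primary intervals.

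Finally, the shortfall is conditional. It needs an ICC above 0 and a target beyond the sites studied. The sites were chosen from control neighborhoods of an earlier trial with a willing partner (Section 5.1), and Section 9.4.2 claims no wider population of sites. An interval that describes only these sites is defensible if it is labelled so. At present it is not.

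**Conclusion.** The point stands in conditional form. No allowance for site is stated for the primary intervals, the planned margin reproduces only with independent youth, and each arm is two sites. If the intervals are computed that way, coverage beyond those sites falls from a nominal 95% to between about 94% (ICC 0.01) and 71% (ICC 0.20). These ICCs are assumed, site sizes are taken as near equal, and the simulations use a normal outcome. At ICC 0 the intervals are right, so it cannot be said that they will certainly be too narrow.

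A reader might infer that the trial's inference is invalid. The documents do not support this: there is no primary between-arm test and no numerical threshold for going on to a larger trial, so no stated decision would flip. The harm is overstated precision in the figures that inform the next trial. The plan should be changed because the primary result is exactly this interval and the remedy is cheap. The 0.20 margin in Section 9.2 has the same cause and should not be counted as a separate major defect.

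**What to change.** In Section 9.4.2:

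1. Report attendance and satisfaction by site beside each arm figure (four youth sites, two adult sites).
2. Give the arm interval with its standard error multiplied by √(1 + (m − 1) × ICC) over a stated ICC range, for example 0.01 to 0.10. A range is needed because two sites cannot estimate the site variance reliably. The widening restores coverage only where the assumed ICC is near the true one.
3. Label any unadjusted interval as describing those sites only.
4. State whether the mixed-model sentence in Section 9.4.1 covers the primary endpoints.

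Section 9.2 should show its margin over the same range: 0.207 at ICC 0.01 to 0.287 at ICC 0.10, against 0.196 with no clustering.

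The cost is some wording and a few table rows, with no new data or participants. The downside is that reported intervals become about 6% to 47% wider over ICC 0.01 to 0.10 (√1.115 = 1.06, √2.15 = 1.47).
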